6.5. Assessments for Subjects who Reach Kidney Failure While on Study Drug

Subjects who reach kidney failure will be instructed to discontinue study drug, complete the EOT and 30 Day (± 7 days) EOT Follow-up visits, which will include an assessment of eGFR and UACR. Following the 30 Day EOT Follow-up visit, subjects who reach kidney failure will continue on study, followed via remote assessments per Section 6.7.3, but no longer followed for the primary efficacy endpoint.

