8.9. Sample Size

8.9.1. Sample Size Determination

With a sample size of 300 subjects (150 per treatment arm), power to detect a difference in $eGFR_{cr}$ decline rate of 3.7 mL/min/1.73 m²/year (common SD = 10 mL/min/1.73 m²/year) between SEL 18 mg and placebo using a two-sample t-test is 99% at a 1-sided significance level of 0.15. Assuming 15% dropout, with a sample size of 254 (127 per arm), the power is 97%.

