6.1.3. Analysis of the Primary Endpoint

The Primary Analysis Set for efficacy analyses is the Full Analysis Set.

Definition of Baseline

Baseline eGFR_{cr} for the primary analysis is defined as below:

- SEL arm: The average of the measurements at Visit C and Visit 1. This Baseline will also be referred to as post-run-in Baseline.

- Placebo arm: The average of the measurements at Visit A (enrollment) and Visit B. This Baseline will also be referred to as pre-run-in Baseline.

Estimand

The Treatment Policy estimand is defined as follows. This is the primary estimand for the primary endpoint.

- 1) Population: Subjects in the FAS. See definition of the FAS in Section 3.1.3.
- 2) Variable: Primary endpoint (eGFR_{cr} slope from treatment-specific Baselines through Week 84). See Section 6.1.1 for detailed definition of the primary endpoint.
- 3) Intercurrent events: Intercurrent events for this study include study treatment discontinuation and/or starting a concomitant medication (e.g. SGLT-2 inhibitors).

The occurrence of an intercurrent event is irrelevant. All observed values will be used regardless of occurrence of an intercurrent event.

- All observed values will be used regardless of occurrence of an intercurrent event (i.e, All available data defined above)
 - If a subject is lost to follow up, treat data as missing from the point of loss to follow-up onward
- 4) Population-level summary: eGFR_{cr} slope from treatment-specific Baselines through Week 84 in each treatment arm, and difference in eGFR_{cr} slope from treatment-specific Baselines through Week 84 between SEL and placebo treatment arms.

Main Estimator

A random slope model will be used to evaluate SEL treatment effect on eGFR_{cr} slope from treatment-specific Baselines through Week 84. The random slope model will have eGFR_{cr} change from treatment-specific Baselines at Weeks 4, 8, 12, 24, 36, 48, 60, 72 and 84 as outcome, and will include terms for eGFR_{cr} at treatment-specific Baselines as a continuous variable, pre-run-in Baseline UACR category (< 1500 mg/g vs. ≥ 1500 mg/g), concomitant use of SGLT-2 inhibitors at Randomization, treatment group, week, and treatment-by-week interaction. Within-subject variance covariance will be modeled as unstructured. If model convergence problems arise, other variance-covariance structures, such as Heterogeneous Toeplitz, will be considered and documented.

Sensitivity analyses of the eGFR_{cr} slope endpoint will include the following:

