- Sensitivity analysis of eGFR_{cr} slope excluding off-treatment eGFR_{cr} values from the SEL treatment group.

- Sensitivity analysis of eGFR_{cr} slope excluding eGFR_{cr} values collected after the initiation of dialysis or kidney transplantation.
- Sensitivity analysis to evaluate the impact of attenuation of the acute effect. For subjects in the SEL group, the on-treatment eGFR_{cr} values will be adjusted using a regression model as described in [Appendix 2](#), which takes into account attenuation of the acute treatment effect that may be due to the theoretical concern for loss of kidney function over time. For subjects in the placebo group, the observed eGFR_{cr} values will be used. The analysis of eGFR_{cr} slope will be performed using the same model as described in the primary analysis, except that pre-run-in Baseline eGFR_{cr} will be used for both SEL and placebo arms.
- Sensitivity analysis of eGFR_{cr} slope in subjects who completed study treatment.
- Sensitivity analysis of eGFR_{cr} slope excluding subjects with randomization stratification mismatch between IXRS and Clinical Database.
- Sensitivity analysis of eGFR_{cr} slope excluding subjects who took prohibited medications that may affect SEL efficacy or decrease SEL drug level in the prohibited period as detailed in [Appendix 3](#).
- Sensitivity analysis of eGFR_{cr} slope from pre-run-in Baseline for both SEL and placebo arms.
- Sensitivity analysis of eGFR_{cr} slope from treatment-specific Baselines through Week 48.
- Sensitivity analysis of eGFR_{cr} slope from treatment-specific Baselines through Week 60.
- Sensitivity analysis of eGFR_{cr} slope from treatment-specific Baselines through Week 72.
- Sensitivity analysis of eGFR_{cr} slope from treatment-specific Baselines through Week 96.

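### The eGFRcr and eGFRcys slope models keep values taken after dialysis or kidney transplantation, which do not measure native kidney function; these values are removed only in sensitivity analyses

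*SAP*

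**What the plan says.** SAP 6.1.3 sets a treatment policy estimand for the eGFRcr slope through Week 84. It names two intercurrent events: stopping study treatment, and starting another drug such as an SGLT-2 inhibitor. The data rule is "All observed values will be used regardless of occurrence of an intercurrent event". Protocol 8.5.1.1 likewise admits both on- and off-treatment eGFRcr after Visit 1.

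Dialysis and transplantation affect the slope in one place only, a sensitivity analysis that drops eGFRcr "values collected after the initiation of dialysis or kidney transplantation". SAP 6.2.2.3 has the matching sensitivity analysis for eGFRcys.

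Under Protocol 6.5, a subject who reaches kidney failure on study drug stops the drug and has an EOT visit and a 30 Day EOT Follow-up visit. Appendix 2 schedules eGFR at both. The subject then moves to remote contact and stays in the study, "but no longer followed for the primary efficacy endpoint". Kidney failure (Protocol 3.1, SAP 6.2.1) has three routes: dialysis lasting 4 weeks or more, transplantation, or confirmed eGFR below 15 with neither.

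**The concern.** The primary objective concerns decline in kidney function. On dialysis, serum creatinine is partly set by the dialysis; after transplantation it is set by the graft. Neither describes the diseased kidneys. Treatment policy is reasonable after a subject stops the drug, because eGFR still measures the same organ. It does not rescue a measurement whose meaning has changed.

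These values will occur. A subject who fails by the dialysis route while on drug has already had 4 weeks of dialysis before the EOT and follow-up samples are drawn. SAP 3.8.2 assigns samples to visits by study day, so they can fill a late visit slot, where leverage on a slope is high. The values then enter the test that decides the trial, and a secondary test at the same one-sided 0.15 level.

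**Working it through.** **1. The plan's own figure.** Inputs from Protocol 8.9.1: difference 3.7, SD 10, one-sided 0.15 (z = 1.036).
- 150 per arm: SE = 10 × √(2/150) = 1.155; 3.7/1.155 − 1.036 = 2.168; power 98.5%.
- 127 per arm: SE = 10 × √(2/127) = 1.255; 3.7/1.255 − 1.036 = 1.912; power 97.2%.

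The Protocol's statement for 150 per arm is "using a two-sample t-test is 99% at a 1-sided significance level of 0.15", and it gives 97% for 127 per arm. Both reproduce to within a point. The calculation does not involve the dialysis rule; 3.7 and 1.155 serve below as yardsticks.

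**2. How many subjects and values.** In the earlier Phase 2 study (Protocol 1.2.3.2.2), 4 placebo and 13 SEL subjects stopped drug for progression to ESKD: 17/333 = 5.1% in 48 weeks. At a constant rate to Week 84 this is 1 − (1 − 0.051)^(84/48) = 8.8%. The simulation therefore used 2%, 5% and 9% of an arm.

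Analysis windows from Week 24 onward are 84 days wide (SAP Table 3-2). If timing is uniform, two visits 30 days apart share a window with probability (84 − 30)/84 = 64%. Where SAP 3.8.3 requires a single record, only one is then kept. More than two values could arise for dialysis shorter than 4 weeks, or for a subject who stopped drug earlier and still attends full visits, because Protocol 6.5 is written for failure on study drug.

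**3. Keeping versus deleting the values.** One arm of 150 was simulated at Weeks 4 to 84 and fitted by GLS with a random intercept and slope, with and without post-event values. Mean slopes of −4.97 and −1.27 are the placebo and SEL 18 mg values in Protocol Table 1-2. These inputs are assumptions, not in the documents:
- random-intercept SD 3, random-slope SD 6, residual SD 4, variance components treated as known;
- baseline eGFR uniform 20 to 59;
- replacement therapy in the subjects with the lowest projected Week 84 eGFR, starting after Weeks 24 to 72;
- the post-event values shown in the table.

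Each scenario had 60 replicates. The table gives the change in the arm's slope (mL/min/1.73 m²/year) from keeping two post-event values per subject. Each cell shows the result for mean slope −4.97, then −1.27.

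| Post-event eGFR | 2% of arm | 5% | 9% |
|---|---|---|---|
| Transplant, 50 | +0.55 / +0.47 | +1.35 / +1.23 | +2.29 / +2.05 |
| Dialysis, 12 | +0.01 / −0.03 | −0.01 / −0.17 | −0.16 / −0.40 |
| Dialysis, 7 | −0.04 / −0.09 | −0.17 / −0.37 | −0.46 / −0.70 |
| Dialysis, 5 below last value | −0.04 / −0.06 | −0.10 / −0.17 | −0.20 / −0.32 |

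Across one, two or all remaining visits, the range is +0.35 to +2.40 for transplants and −0.70 to +0.07 for dialysis. Dialysis values mostly steepen the slope because they stay far below baseline.

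**4. Net effect on the treatment difference.**
- Transplant: 2% of 150 is 3 subjects, so each contributes 0.47/3 = 0.16 to 0.55/3 = 0.18. An imbalance of one transplant moves the difference by 0.16/3.7 = 4% to 0.18/3.7 = 5% of the design difference, or about 0.14 to 0.16 of a standard error.
- Dialysis: 5% of 150 is 7.5 subjects. An imbalance of four gives between 4 × (−0.01/7.5) = −0.01 and 4 × (−0.37/7.5) = −0.20.
- Equal counts need not cancel exactly. At 5% in both arms with dialysis values of 7, the SEL-minus-placebo difference changes by −0.37 − (−0.17) = −0.20.

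**The case against.** The strongest reply is that treatment policy is declared openly, that the exclusion is already pre-specified for both slopes, and that kidney failure is counted directly in the two Kidney Clinical Event endpoints. On this view, which version leads is a choice of estimand in a Phase 2b trial.

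The numbers affected are also likely to be low. The Phase 2 rate counts drug stops for ESKD, not dialysis or transplants, and that study included subjects with baseline eGFR below 20. This trial requires screening eGFR of at least 20 and at least 15 throughout run-in, and it excludes anticipated ESKD within 3 months. A subject who passes through confirmed eGFR below 15 first stops drug and generally goes to remote contact before any dialysis value could be drawn. All of this stands as regards size. It does not make a graft's eGFR a measure of the endpoint, and a sensitivity analysis does not decide the primary test.

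A reader might infer something stronger: that kidney failures improve the slope of the arm in which they occur, so that a working drug is penalised and a harmful one flattered. The documents do not support this. Confirmed eGFR below 15 without replacement therapy is true native decline and correctly steepens the slope. Only transplantation flattens it consistently.

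For dialysis, an upward shift appears only when the measured value is compared with an unobserved, lower native value. Suppose the last one or two of eight values (Weeks 4 to 72) are raised by 3 to 8 mL/min. Ordinary least squares then gives +1.4 to +6.1 per subject. For eight subjects this is 8 × 1.4/150 = +0.07 to 8 × 6.1/150 = +0.33 for the arm. No document gives that rise, and the remedy deletes the values instead of replacing them. Against deletion, the sign is mostly the opposite.

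Nor does Protocol 6.5 show that the EOT and follow-up values were meant to be excluded. It ends primary-endpoint follow-up after those visits, which limits how many such values exist.

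**Conclusion.** The point holds as a defect in the estimand and the slope models. Followed as written, the plan puts values that do not measure native kidney function into the primary eGFRcr slope and the secondary eGFRcys slope, and it names neither dialysis nor transplantation as an intercurrent event. The bias is upward for transplant, of uncertain sign and usually toward a steeper slope for dialysis, and absent for confirmed eGFR below 15 without replacement therapy.

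The net effect is probably small: about 0.16 to 0.18 mL/min/1.73 m²/year per transplant of imbalance, and at most about 0.20 in the dialysis cases of step 4, against 3.7. A cluster of transplants in one arm would matter more. These sizes rest on the assumed event rates, post-event values and variance components. The simulation used a simpler model than the SAP's, which takes change from baseline with an unstructured covariance. It was not run for eGFRcys, so for that endpoint the point is qualitative.

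**What to change.** In SAP 6.1.3 and 6.2.2.3:
- list initiation of dialysis and kidney transplantation as intercurrent events;
- exclude eGFR values collected after either event from the main slope models;
- keep all native values, including those below 15 before replacement therapy;
- move the all-values version to the sensitivity list.

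This swaps analyses that are already specified, needs no new data and leaves the stated power unchanged. Because Protocol 8.5.1.1 includes all off-treatment values, the SAP should record the change as a departure from the Protocol, and it should be made before unblinding.

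The cost is that a few late values are lost and the model relies on missing-at-random after replacement therapy starts. The all-values sensitivity analysis and the Kidney Clinical Event endpoints help to check that assumption.

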6.2. Secondary Endpoints

6.2.1. Definition of Secondary Endpoints

Secondary endpoints for this study are:

- Proportion of Kidney Clinical Events defined as any of the following events:
 - Confirmed $\geq 40\%$ decline in eGFR_{cr} from pre-run-in Baseline, or
 - Kidney failure (dialysis performed for at least 4 weeks, kidney transplantation, or confirmed decrease in eGFR_{cr} to < 15 mL/min/1.73 m² for subjects without dialysis or kidney transplantation), or
 - Death due to kidney disease

The $\geq 40\%$ decline in $eGFR_{cr}$ from Baseline and sustained decrease in $eGFR_{cr}$ to <15 mL/min/1.73 m² components need to be confirmed at the next scheduled visit but at least 4 weeks after the index measurement (i.e., the first measurement of $\geq 40\%$ decline in $eGFR_{cr}$ from Baseline or $eGFR_{cr} < 15$ mL/min/1.73 m²). Events of $eGFR_{cr}$ decline $\geq 40\%$ from Baseline or $eGFR_{cr} < 15$ mL/min/1.73 m² without confirmation due to study discontinuation (e.g., death or lost to follow-up) will be included in the analysis and counted as events. Date of the index measurement will be used as the date of event in the analysis.

- Time from randomization to first occurrence of a Kidney Clinical Event

If a subject has not experienced any Kidney Clinical Events at the time of global study end date/early discontinuation of the study, this subject will be censored at the time of the last assessment of kidney function.

- $eGFR_{cys}$ slope from pre-run-in Baseline through Week 84

The values for $eGFR_{cys}$ will be calculated using the CKD-EPI Cystatin C Equation (2012):

$$eGFR = 133 \times \min\left(\frac{S_{cys}}{0.8}, 1\right)^{-0.499} \times \max\left(\frac{S_{cys}}{0.8}, 1\right)^{-1.328} \times 0.996^{Age} \times 0.932[if\ female]$$

S_{cys} = standardized serum cystatin C (mg/L)

min indicates the minimum of $S_{cys}/0.8$ or 1

max indicates the maximum of $S_{cys}/0.8$ or 1

age in years

6.2.2. Analysis of Secondary Endpoints

The Secondary Analysis Set for efficacy analyses is the Full Analysis Set.

6.2.2.1. Analysis of proportion of Kidney Clinical Events

Number and proportion of subjects who experience a Kidney Clinical Event will be summarized by treatment group. Number and proportion of subjects who experienced each component of the Kidney Clinical Events will also be summarized by treatment group. 95% exact CI based on the Santner-Snell method (Santner and Snell, 1980) will be presented for the difference in proportions between SEL and placebo arms for the Kidney Clinical Events endpoint, as well as each component of the Kidney Clinical Events.

P-value based on the Cochran-Mantel-Haenszel (CMH) approach adjusting for randomization stratification factors will be reported for the comparison of proportion of Kidney Clinical Events between treatment arms. In addition, p-value based on Fisher's exact test without adjusting for randomization stratification factors will also be reported. P-values will not be reported for the comparison of each component of the Kidney Clinical Events endpoint between treatment arms.

Subjects who do not have sufficient measurements to determine whether or not they had a Kidney Clinical Event will be considered not having a Kidney Clinical Event.

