1.3. Sample Size and Power

With a sample size of 300 subjects (150 per treatment arm), power to detect a difference in $eGFR_{cr}$ decline rate of 3.7 mL/min/1.73 m^2 /year (common SD = 10 mL/min/1.73 m^2 /year) between SEL 18 mg and placebo using a two-sample t-test is 99% at a 1-sided significance level of 0.15. Assuming 15% dropout, with a sample size of 254 (127 per arm), the power is 97%.

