3.5. Multiple Comparisons

The study has 1 primary efficacy endpoint: eGFR_{cr} slope from treatment-specific Baselines. The primary endpoint and each secondary endpoint will be evaluated at a 1-sided Type 1 error level of 0.15. No formal multiplicity adjustment will be performed. All other efficacy endpoints will also be tested using 1-sided tests at the 0.15 significance level without multiplicity adjustment.

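### The planned Santner-Snell interval for the difference in Kidney Clinical Event proportions is likely to be far too wide at low event rates, most of all for the rare components

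*SAP*

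**What the plan says.** SAP 6.2.2.1 plans a "95% exact CI based on the Santner-Snell method" for the difference in the proportion with a Kidney Clinical Event, "as well as each component of the Kidney Clinical Events". It does not mention strata for this interval, and it does not say which form of the method or which software option will be used.

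Two tests of the composite proportion follow in the same section. For the first, "P-value based on the Cochran-Mantel-Haenszel (CMH) approach adjusting for randomization stratification factors will be reported". The second is Fisher's test: an "exact test without adjusting for randomization stratification factors will also be reported". Section 6.2.2.1 gives no p-values for the components.

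SAP 3.5 sets the decision level: "The primary endpoint and each secondary endpoint will be evaluated at a 1-sided Type 1 error level of 0.15". SAP 6.2.2.2 provides a stratified Cox hazard ratio with a 95% CI for the composite and each component, but only where an outcome has more than 10 events and at least one in each arm. Protocol 8.5.2.1 specifies the CMH test and no interval for the difference.

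**The concern.** An exact unconditional interval must protect its level at every value of the unknown background event rate. When it is built on the raw difference in proportions, the worst case is a rate near 50%, where the binomial variance is largest. The limits are set for that case and do not narrow when events are rare.

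The absolute risk difference is how a reader will judge the size of any effect on this secondary endpoint. If the interval is much wider than the data warrant, the effect looks less well estimated than it is, and the interval may appear to contradict the p-value beside it. The distortion grows as events become rarer, so it is worst for the components. The 6.2.2.1 approach is also carried into the sensitivity analyses and the Week 48 analysis.

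**Working it through.** **Inputs.** Arm size comes from SAP 1.3: "With a sample size of 300 subjects (150 per treatment arm"). The nominal level is 95% two-sided (SAP 6.2.2.1). The event rate is not given for this composite, so it is assumed and varied. The nearest documented figure is study drug discontinuation for progression to ESKD in the earlier 48-week study: 4.7% on placebo and 5.2% on pooled SEL (Protocol 1.2.3.2.2). The present composite is broader because it also counts a confirmed 40% eGFR decline. The Santner-Snell form is assumed to be the tail method: two one-sided 2.5% exact unconditional tests on the raw difference, with the tail probability maximised over the background rate.

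**The plan's own figures.** The plan states no power, event rate or interval width for this endpoint; 95% is the only figure to check. The sample size statement that supplies the 150 per arm reproduces: 98.5% and 97.2%, against the stated 99% and 97%.

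**Step 1: width.** At the worst-case rate the normal approximation to the half-width is

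1.96 × √(2 × 0.5 × 0.5 / 150) = 1.96 × 0.0577 = 0.113.

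The exact discrete calculation gives about 0.116, so the full width is about 0.232 at any event rate.

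**Step 2: coverage, by hand.** At a true common rate p, the standard error of the difference is √(2p(1−p)/150).

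- p = 20%: SE = √(2 × 0.2 × 0.8 / 150) = 0.0462, and 0.116 / 0.0462 = 2.51 standard errors, or about 98.8% coverage.
- p = 5%: SE = √(2 × 0.05 × 0.95 / 150) = 0.0252, and 0.116 / 0.0252 = 4.6 standard errors, or more than 99.99%.

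**Step 3: exact enumeration, 150 per arm, equal rates.** MN is the Miettinen-Nurminen score interval.

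| Event rate (assumed) | Santner-Snell coverage | MN coverage | MN mean width | Width ratio |
|---|---|---|---|---|
| 5% | 99.999% | 95.2% | 0.107 | 2.17 |
| 10% | 99.92% | 95.0% | 0.140 | 1.66 |
| 15% | 99.5% | 95.1% | 0.164 | 1.41 |
| 20% | 98.9% | 95.0% | 0.182 | 1.27 |
| 30% | 97.3% | 95.0% | 0.207 | 1.12 |

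At 40% and 50% the ratios are 1.05 and 1.03. At 127 per arm the ratios are nearly the same. With slightly unequal arms (151 and 148), coverage is 99.998% at 5% and 98.6% at 20%. Coverage was not below 95% at any rate tried.

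**Step 4: illustrative tables, SEL v placebo, 150 per arm.**

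| Events | Planned interval | Score interval | Fisher p (two-sided) |
|---|---|---|---|
| 20 v 30 | (−0.182, 0.050) | (−0.152, 0.018) | – |
| 12 v 26 | (−0.208, 0.023) | (−0.171, −0.019) | 0.023 |
| 2 v 12 | (−0.182, 0.050) | (−0.123, −0.022) | 0.011 |
| 0 v 16 | (−0.221, 0.010) | – | 0.00002 |

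For 20 v 30 the width ratio is 0.232 / 0.170 = 1.36. It is 1.27 for 24 v 36, 1.61 for 12 v 20 and 2.27 for 5 v 8.

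**Step 5: how much is due to the strata.** The width of a stratified interval relative to an unstratified one is about √(within-stratum variance / total variance). With assumed stratum sizes and one- to three-fold risk gradients across the eGFR and UACR strata, this ratio runs from 1.00 to 0.94. Stratifying therefore saves about 0 to 6%. Nearly all the excess comes from the unstandardised statistic.

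**Step 6: exactness itself is not the cause.** A Chan-Zhang interval is also exact and unconditional but uses the score statistic. Its width is 0.113 for 8 v 8 events, 0.142 for 15 v 15 and 0.185 for 30 v 30, against about 0.232 for Santner-Snell.

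**The case against.** The strongest defence is that an exact interval promises at least 95%, and this one keeps the promise. Preferring guaranteed coverage to average coverage near 95% is a legitimate choice, and the error is towards caution. That stands, so a reader should not infer that the 95% label is false. It does not defend this particular interval, because Chan-Zhang gives the same guarantee at about half the width when events are rare.

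The event rate is unknown. The SAP endpoint is not confined to Week 48 and its visit windows run to Week 168, so a composite rate above 20% cannot be excluded, and from 30% the excess is small. This also stands. It rules out the tempting summary that the interval really covers 99%: that figure fits rates of about 15% to 20% only, and the two-fold widths occur where coverage is above 99.99%.

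The interval drives no decision. Testing is by p-value, and SAP 6.2.2.2 supplies a stratified hazard ratio. This is correct, so no conclusion of the trial turns on it. But the hazard ratio is withheld at 10 or fewer events or with none in one arm, which is where the planned interval is worst.

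The unstratified interval also has an unstratified exact partner in Fisher's test. That answers a complaint about strata alone, but not the disagreement at 0 v 16, where Fisher's p is 0.00002 and the interval includes zero. Some disagreement with the CMH decision would remain under any 95% interval, since a one-sided 0.15 test pairs with a two-sided 70% interval (1 − 2 × 0.15). That is a separate matter.

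Finally, an asymptotic stratified interval over 12 strata may fall short when events are sparse. A simulated Mantel-Haenszel interval (assumed 150 per arm, 5 to 27 per arm in each stratum) covered about 92% at rates of 1% v 3%. This stands and limits the fix to the composite.

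**Conclusion.** The point holds as one of precision and presentation on a secondary endpoint. Under the raw-difference tail method at 150 per arm, the interval is about 0.23 wide at any event rate. For assumed rates of 20% down to 5% it covers about 98.9% to 99.999% and is about 1.3 to 2.2 times as wide as a score interval, reaching 2.3 times for a component with 5 v 8 events. At 30% or more the excess is about 12% or less. The size rests on two assumptions that the documents do not settle: the form of Santner-Snell to be used and the event rate.

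A reader might infer that the missing stratification is the main fault. The arithmetic does not support that: under the assumed risk gradients it accounts for about 0 to 6% of width. Nor do the documents support a claim that any test, error rate or decision is affected.

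**What to change.** In SAP 6.2.2.1, replace the Santner-Snell sentence with two rules.

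- **Composite:** report a stratified risk difference with a stratified Miettinen-Nurminen (or Mantel-Haenszel) 95% interval, using the strata of the CMH test.
- **Sparse components, including any with no events in an arm:** report an exact unconditional 95% interval based on the score statistic (Chan-Zhang). The SAP should define sparse in advance; the event-count rule already in 6.2.2.2 is one candidate.

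Name the form and the software option in either case, and apply the same rules to the sensitivity and Week 48 analyses. The cost is a sentence or two in the SAP and a different procedure option. No endpoint, test or sample size changes. The downside is that the composite interval is no longer guaranteed exact. In the unstratified calculation, the score interval covered 95.0% to 95.2% at rates of 5% to 30%.

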1.2.3.2.2. Subject Disposition

Of the 334 randomized subjects, 333 subjects received at least 1 dose of study drug: 85 subjects received placebo and 248 subjects received SEL (81, 84, and 83 subjects received SEL 2, 6, and 18 mg, respectively).

A total of 256 subjects (76.9%) completed treatment and 76 subjects (22.8%) discontinued study drug (19 subjects [22.4%] in the placebo group and 57 subjects [23.0%] in the pooled SEL group [18.5%, 21.4%, and 28.9% for SEL 2, 6, and 18 mg, respectively]). The most frequent reason for discontinuation of study drug was due to an adverse event ([AE], 4 subjects [4.7%] in the placebo group and 18 subjects [7.3%] in the pooled SEL group), followed by progression to end stage kidney disease (ESKD) (4 subjects [4.7%] in the placebo group and 13 subjects [5.2%] in the pooled SEL group), and withdrawal of consent (3 subjects [3.5%] in the placebo group and 13 subjects [5.2%] in the pooled SEL group).

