- Sensitivity analysis to evaluate the impact of attenuation of the acute effect. For subjects in the SEL group, the on-treatment $eGFR_{cr}$ values will be adjusted using a regression model as described in [Appendix 2](#), which takes into account attenuation of the acute treatment effect that may be due to the theoretical concern for loss of kidney function over time. This adjusted on-treatment $eGFR_{cr}$ value will be compared with the pre-run-in Baseline $eGFR_{cr}$ to calculate an adjusted percent $eGFR_{cr}$ reduction. For subjects in the placebo group, percent $eGFR_{cr}$ reduction will be calculated by comparing observed $eGFR_{cr}$ values with the pre-run-in Baseline $eGFR_{cr}$.
- Sensitivity analysis in subjects who completed study treatment.
- Sensitivity analysis excluding subjects with randomization stratification mismatch between IXRS and Clinical Database.
- Sensitivity analysis excluding subjects who took prohibited medications that may affect SEL efficacy or decrease SEL drug level in the prohibited period as detailed in [Appendix 3](#).

- Sensitivity analysis where a 57% reduction in $eGFR_{cr}$ from pre-run-in Baseline will be used for the $eGFR_{cr}$ reduction component of the Kidney Clinical Events instead of 40% reduction.
- Sensitivity analysis for the Kidney Clinical Events based on $eGFR_{cys}$. The Kidney Clinical Events endpoint will have the same definition as in Section 6.2.1, except that the $eGFR$ reduction and $eGFR < 15$ components will be based on $eGFR_{cys}$ instead of $eGFR_{cr}$.

The same approaches as described in Sections 6.2.2.1 only will be used for hypothesis testing for Kidney Clinical Events for the following:

- The proportion of Kidney Clinical Events by Week 48 will be compared between SEL and placebo treatment arms. Subjects who do not have sufficient measurements to determine whether or not they had a Kidney Clinical Event by Week 48 will be considered not having a Kidney Clinical Event by Week 48.

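### Counting insufficient kidney data as no event makes the error rate of the Kidney Clinical Event proportion test depend on loss by arm, and no planned analysis checks this

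*SAP*

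**What the plan says.** SAP 6.2.2.1 assigns subjects whose measurements cannot settle their status to the event-free group: they "will be considered not having a Kidney Clinical Event". SAP 6.2.2.2 repeats this for the Week 48 version, where they "will be considered not having a Kidney Clinical Event by Week 48". The SAP does not define how much data is sufficient.

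The rule has an exception. Under SAP 6.2.1, a decline of at least 40% or an eGFR below 15 left "without confirmation due to study discontinuation (e.g., death or lost to follow-up) will be included in the analysis and counted as events".

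The resulting proportion is tested formally. SAP 6.2.2.1 states: "P-value based on the Cochran-Mantel-Haenszel (CMH) approach adjusting for randomization stratification factors will be reported". SAP 3.5 adds: "The primary endpoint and each secondary endpoint will be evaluated at a 1-sided Type 1 error level of 0.15", without multiplicity adjustment.

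The companion time-to-event endpoint uses the same composite but censors event-free subjects at their last kidney assessment (SAP 6.2.1).

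Protocol 3.1 and 8.5.2.1 set the proportion at Week 48 and do not contain the missing-data rule. SAP 6.2.1 gives the proportion no time point, and Week 48 appears only among the sensitivity analyses in SAP 6.2.2.2.

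**The concern.** The rule is single imputation of the favourable outcome. A subject lost early is credited with staying event-free for the whole period, so each arm's observed risk falls in proportion to the kidney data it loses. If the arms lose different amounts, the observed proportions differ even when the true risks are equal.

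Missing eGFR is realistic here. Two routes to an event rest on central-laboratory eGFR, and remote follow-up (Protocol 6.7.3) collects death, transplant and dialysis but no eGFR. The plan allows for 15% dropout, and SAP 4.4 describes visits missed because of COVID-19.

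The SAP also treats the same subject in two ways, censored in one secondary endpoint and event-free in the other. Because each endpoint is tested separately, a result on the proportion could be claimed by itself. The listed sensitivity analyses change the event definition, the population or the time point. None changes how missing data are handled. The treatment-completer analysis changes the population and selects on something that happens after randomization.

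**Working it through.** **The plan's own figure.** Power is stated only for the primary slope. With a difference of 3.7, SD 10 and one-sided 0.15 (z = 1.036), power is Φ(3.7 / (10·√(2/n)) − 1.036).
- n = 150: Φ(3.204 − 1.036) = 0.985 (stated 99%).
- n = 127: Φ(2.948 − 1.036) = 0.972 (stated 97%).

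Both reproduce. No event risk or power is given for the proportion.

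**Inputs for the proportion**
- 150 per arm (SAP 1.3) and one-sided 0.15 (SAP 3.5).
- True event risk p, equal in both arms: 10%, 20% or 30% (assumed).
- Share L of each arm with lost kidney data: assumed. The 15% in SAP 1.3 is not split by arm. The pair 22.4% and 28.9% is drug discontinuation on placebo and 18 mg in the earlier Phase 2 study (Protocol 1.2.3.2.2), used only as one possible split.
- Share m of lost subjects' events that go unseen: 0.5 (loss spread over follow-up) or 1 (an upper bound).

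**Formula.** Observed risk is p·(1 − m·L). The rejection probability for a pooled two-proportion z-test, an unstratified stand-in for CMH, is Φ([(pP − pS) − 1.036·se0] / se1). Here se0 uses the pooled risk and se1 the separate risks.

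**Worked case.** p = 0.20, m = 0.5, loss 22.4% on placebo and 28.9% on SEL:
- pP = 0.20·(1 − 0.112) = 0.1776
- pS = 0.20·(1 − 0.1445) = 0.1711
- se0 ≈ se1 ≈ 0.0438
- (0.0065 − 0.0454) / 0.0438 = −0.888, so Φ = 0.187

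**Type I error with m = 0.5**

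| Loss, placebo / SEL | p = 10% | p = 20% | p = 30% |
|---|---|---|---|
| 15% / 15% | 0.150 | 0.150 | 0.150 |
| 12% / 18% | 0.172 | 0.183 | 0.194 |
| 22.4% / 28.9% | 0.174 | 0.187 | 0.199 |
| 10% / 20% | 0.188 | 0.208 | 0.228 |
| 20% / 10% | 0.118 | 0.104 | 0.092 |
| 28.9% / 22.4% | 0.128 | 0.118 | 0.110 |

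The bias in the risk difference, p·m·(difference in loss), has a size of 0.10·0.5·0.06 = 0.3 points to 0.30·0.5·0.10 = 1.5 points. With m = 1 the 22.4% / 28.9% row becomes 0.206, 0.236 and 0.264.

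**Simulation check** (6,000 null trials per case, exponential events, random loss). At 22.4% / 28.9% the crude test rejected in 0.171, 0.187 and 0.200 of trials. On the same data a log-rank test with censoring at loss rejected in 0.142, 0.146 and 0.147. Across the simulated splits an unstratified Kaplan-Meier difference stayed at 0.14 to 0.16.

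**Equal loss.** With 15% loss and m = 0.5, a true 10-point difference is seen as 10·(1 − 0.075) = 9.25 points. For risks of 20% and 12%, power falls from 0.805 to 0.780.

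**Strata.** The factors give 3 × 2 × 2 = 12 strata (SAP 3.3), so 300/12 = 25 subjects per stratum and 12 or 13 per arm if spread evenly. In a simulation of a Greenwood test weighted over all 12, 9% to 44% of stratum-arm cells had zero variance, and type I error was 0.15 to 0.18.

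**The case against.** A reader might infer three stronger things.

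**That every subject with incomplete data is called event-free.** The documents do not support this. Unconfirmed index events at study discontinuation count as events. Off-drug subjects are asked to keep full visits (Protocol 6.7.1), limited follow-up still measures eGFR every 12 weeks (6.7.2), and remote follow-up still records dialysis, transplant and death (6.7.3).

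**That the test is inflated.** This holds only if SEL loses more unseen events. With equal loss the error rate is 0.15, and with more loss on placebo the test is conservative.

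**That the direction favours SEL**, because Phase 2 drug discontinuation was "18.5%, 21.4%, and 28.9% for SEL 2, 6, and 18 mg, respectively", against 22.4% on placebo. That is discontinuation of drug, not loss of kidney data, and progression to ESKD was among the leading reasons. The two lower doses were below placebo, and 24/83 against 19/85 gives a two-sided Fisher p of 0.38. In the present trial everyone takes SEL in the run-in, and those who permanently stop are not randomized (Protocol 4.4). An opposing bias also exists. The 40% decline is counted from the pre-run-in baseline, while SEL causes a median 10% acute fall (Protocol 7.5.5). In the worked case, one extra percentage point of true SEL events lowers 0.187 to 0.139.

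Two further defences carry less weight. Fisher's p-value is also reported and, at 22.4% / 28.9%, a simulation put its rejection rate at 0.12 to 0.16. But Protocol 8.5.2.1 names CMH as the hypothesis test, and a conservative test does not remove bias from the estimate. The time-to-event endpoint handles follow-up properly, and a reader can compare the two results, but the proportion keeps its own claim at 0.15. Nor can the acute eGFR effect be relied on to cancel a separate bias of unknown size.

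**Conclusion.** The point holds conditionally. The rule ties the error rate of the one-sided 0.15 test to the balance of lost kidney data. With half of lost subjects' events unseen, the rate is 0.15 for equal loss. It is 0.17 to 0.21 in eight of the nine cases where SEL loses more, and 0.23 in the ninth. It is 0.09 to 0.13 where placebo loses more. Equal loss leaves the error rate alone but understates risk and weakens a real difference.

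These figures rest on assumed event risks and loss splits, loss unrelated to prognosis, and an unstratified stand-in for CMH. Loss by arm is not in the documents, so neither inflation nor its direction can be asserted for this trial. What can be asserted is that the rule is stated, feeds a formal test, differs from the censoring used for the same composite, and is not varied in any listed analysis. It should be changed. It affects a secondary endpoint and does not touch the primary slope analysis.

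**What to change.** - **Main estimate:** the proportion at Week 48, the protocol's time point, as one minus Kaplan-Meier in each arm with the SAP 6.2.1 censoring rule. Alternatively, use cumulative incidence with non-kidney death as a competing event, since Kaplan-Meier treats such deaths as censoring and overstates incidence.
- **Test:** the difference between arms, unstratified or with collapsed strata, because 12 strata leave sparse cells.
- **Sensitivity analyses:** keep the current CMH analysis with missing counted as no event, and add a tipping-point analysis for informative loss.
- **Reporting:** define sufficient measurements, and tabulate subjects with insufficient data by arm so that the balance is visible.

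The cost is SAP wording and modest programming, with no new data. The main estimate would assume non-informative censoring, which is why the tipping-point analysis is needed. If the SAP is already final, SAP section 1 requires the change to be documented in the CSR.
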